| Study Design: This is a phase II, randomized, double-blind, active comparator, parallel group study to evaluate the efficacy and safety of K-285 compared with menthol gel for the treatment of delayed onset muscle soreness (DOMS) in the lower extremity. The study will consist of screening, an exercise visit (DOMS induction), in-patient and out-patient periods up to 3 weeks, and a follow-up telephone call. During the Screening Visit, subjects will provide informed consent and complete screening assessments including medical history, identification of the dominant leg, physical and skin examinations, blood and urine tests, vital signs measurements, electrocardiogram (ECG), and other screening procedures. Subjects who are able to participate in the study (Period 1 and 2) and who meet the pre-exercise inclusion and exclusion criteria will be enrolled into the study and return to the clinic on Day -1. Eligibility will be confirmed and enrolled subjects will perform a standardized repetitive quadriceps muscle exercise to create DOMS to both legs (Day -1). The exercise regimen will consist of a warm-up, determination of maximum tolerated weight, and timed and un-timed workout phases. Within 24 to 30 hours after the exercise session (Day 1), subjects will rate the pain of both legs using a categorical pain scale and record pain intensity of both legs at rest and while standing using a 0-100 point electronic visual analog scale (eVAS) (a capture program will linearly convert the pixel touched to an integer between 0 and 100) to determine eligibility for randomization. The specific post-exercise [REDACTED] inclusion criterion will be masked to subjects. [REDACTED] [REDACTED]. If both legs meet post-exercise inclusion criteria, the study leg will be the dominant leg, based on hand dominance. Subjects not qualifying for randomization will be given appropriate standard of care. A total of 240 subjects who meet post-exercise inclusion criteria will be randomly assigned in a 1:1 ratio to Treatment Arm A (K-285 gel) or Treatment Arm B (Menthol gel). [REDACTED] [REDACTED] [REDACTED] [REDACTED] | | | |

[REDACTED]

In Period 1 [REDACTED] study gels will be applied to randomized subjects on a [REDACTED] [REDACTED] [REDACTED] on the study leg as follows:

- Treatment Arm A: Each subject will apply K-285 to the study leg.
- Treatment Arm B: Each subject will apply menthol gel to the study leg.

The first study gel application to the study leg will be applied by the subject with investigator (or designee) oversight to ensure proper application at the clinic on Day 1 within 24 to 30 hours after DOMS induction. Subsequent study gel applications at the clinic will be applied to the study leg by the subject with investigator (or designee) oversight to ensure proper application. On Day 2, photographic and residue evaluation of the application site will be performed prior to the [REDACTED] study gel application. Subjects will remain in the clinic until they are discharged following completion of study assessments on Day 2.

Pain intensity assessments will be performed for the study leg and non-study leg at rest and while standing using a 0-100 point eVAS on Day 1 at Baseline (0 hours) and at [REDACTED]

[REDACTED] after the first study gel application. Pain assessments scheduled between midnight and 6 am may be skipped if subjects are asleep but subjects may not skip more than two sequential assessments. A time window of +30 minutes will be allowed between qualification (baseline assessment) and first gel application (0 hour). The following time windows will be allowed for each pain assessment (eVAS, Perceptible Pain Relief, and Meaningful Pain Relief) time point:

[REDACTED]

Following discharge from the clinic on Day 2, subsequent study gel applications and pain intensity assessments will be performed by the subject on an out-patient basis (Day 2 through Day 8). Subjects will be instructed not to shower or bathe for at least 30 minutes before and at least 1 hour after gel application. All pain intensity assessments including eVAS, Perceptible Pain Relief, and Meaningful Pain Relief will be recorded in e-diaries through Day 8 (Period 1), and all study gel applications and rescue medications will be recorded in the e-diary by the subject through Day 22 (Period 1 and 2). Perceptible Pain Relief and Meaningful Pain Relief will be recorded in the e-diary until achieved in Period 1. A telephone call will be conducted by study staff on Day 5 (± 1 day) to assess safety. Subjects will return to the clinic for assessments on Day 8 (± 1 day). For subjects who are assigned to receive study gel for 1 week, Day 8 end of

study (EOS) (+1 day) will be a clinic visit and a follow-up telephone call to assess safety will be conducted by study staff on Day 15 (± 1 day). Subjects who are assigned to receive study gel for 3 weeks will continue to apply study gel on an out-patient basis from Day 8 to Day 22 (Period 2) according to their assigned dosing regimen (██████████) (Table 1 above). For subjects who are dosing in Period 2, telephone calls to assess safety will be conducted by study staff on Day 11 (± 1 day) and Day 18 (± 1 day), study gel applications and use of any rescue medications will be recorded in e-diaries by the subjects through Day 22, and an end of study (EOS) clinic visit will occur on Day 22 (+1 day). A follow-up telephone call to assess safety will be conducted by study staff on Day 29 (± 1 day).

Use of any rescue medication for DOMS is strongly discouraged until 168 hours (Day 8) after the first study gel application, at which time over-the-counter (OTC) acetaminophen (one 500 mg acetaminophen tablet twice daily, not more than every 6 hours) as rescue medication for DOMS is permitted if required. Subjects experiencing severe pain or inability to move or walk due to pain may be permitted to use rescue medication (one 500 mg OTC acetaminophen tablet twice daily, not more than every 6 hours) prior to 168 hours after the first study gel application. If subjects take rescue medication before the first 168 hours, it will be captured as a concomitant medication, and subjects will record their pain intensity in the e-diary before taking the rescue medication. The number of tablets taken and the date and time will be recorded in the e-diary.

When the ██████████
██████████. The interim analysis will assess futility of the trial (conditional power < 0.05). If futility is determined, the study will be terminated. If continuation of the trial is determined, subject enrollment will be resumed.

Primary Objective:

- To evaluate the efficacy of K-285 compared with menthol gel between 0 to 24 hours after the first gel application for the treatment of DOMS

Secondary Objectives:

- To evaluate the efficacy of K-285 compared with menthol gel after the first gel application for the treatment of DOMS
- To evaluate the safety and tolerability of K-285 compared with menthol gel after the first gel application for the treatment of DOMS

Subject Population:

The study population will be adult male and female subjects aged 18 to 35 years, inclusive, with a body mass index (BMI) between 18 and 32 kg/m², inclusive.

Number of Subjects:

Total 240 subjects with 120 subjects in each of the 2 treatment arms (Table 1 above).

Number of Centers:

1 site in the United States

Dose Levels:

K-285: ██████████

Menthol gel: ██████████

Route of Administration:

Topical gel

Duration of Treatment:

██████████ (Period 1): Each subject will apply ██████████ of study gel ██████████

██████████ (Period 1 and 2): Each subject will apply ██████████ of study gel ██████████ and then will apply study gel ██████████

Criteria for Evaluation:

Efficacy:

Primary Endpoint:

- The sum of pain intensity difference (SPID) between [REDACTED] for the study leg after the first study gel application while standing using a 0-100 point eVAS

Secondary Endpoints:

For both the study leg and the non-study leg

- SPID0-24 hours after the first study gel application at rest using a 0-100 point eVAS
- SPID between 0 (Baseline) to 12 hours (SPID0-12) after the first study gel application while standing using a 0-100 point eVAS
- SPID0-12 hours after the first study gel application at rest using a 0-100 point eVAS
- SPID between 0 (Baseline) to 48 hours (SPID0-48) after the first study gel application while standing using a 0-100 point eVAS
- SPID0-48 hours after the first study gel application at rest using a 0-100 point eVAS
- SPID between 0 (Baseline) to 72 hours (SPID0-72) after the first study gel application while standing using a 0-100 point eVAS
- SPID0-72 hours after the first study gel application at rest using a 0-100 point eVAS

- [REDACTED]
- [REDACTED]
- [REDACTED]
- [REDACTED]
- [REDACTED]
- [REDACTED]
- [REDACTED]
- [REDACTED]
- [REDACTED]
- [REDACTED]
- [REDACTED]
- [REDACTED]
- [REDACTED]
- [REDACTED]
- [REDACTED]
- [REDACTED]
- [REDACTED]

Safety:

Safety assessments will include adverse events (AEs), vital sign measurements (systolic blood pressure, diastolic blood pressure, pulse rate, respiratory rate, and oral body temperature), ECG, physical examination findings including weight, study gel application site reactions, clinical laboratory test results, study gel use, and concomitant medication use.

Criteria for Inclusion:

Pre-exercise Criteria for Inclusion:

1. Subject must provide informed consent before any study-specific evaluation is performed.
2. Subject is male and female aged 18 to 35 years, inclusive.
3. Subject has a body mass index of 18 to 32 kg/m², inclusive
- [REDACTED]
- [REDACTED]
6. Subject hematology, serum chemistry, urinalysis, vital sign measurements (systolic blood pressure, diastolic blood pressure, pulse rate, respiratory rate, and oral body temperature) and 12-lead ECG results show no clinically relevant abnormalities, as judged by the investigator at the Screening Visit.
7. All female subjects must have a negative serum pregnancy test result at screening and negative urine pregnancy test on Day -1 prior to admission to the clinic. Female subjects of childbearing potential must use one of the following acceptable birth control methods as specified before enrollment and throughout the study:
 - a. Surgical sterilization (bilateral tubal ligation, hysterectomy, bilateral oophorectomy) at least 6 months before the first dose of study gel;
 - b. Intrauterine device in place for at least 3 months before the first dose of study gel and throughout the study;
 - c. Barrier method (condom or diaphragm) with spermicide for at least 14 days before the first dose of study gel and throughout the study;
 - d. Surgical sterilization of the male partner (vasectomy at least 6 months before the first dose of study gel);
 - e. Hormonal contraceptives for at least 3 months with a barrier method 14 days before the first dose of study gel and throughout the study;
 - f. Abstinence.
8. Subject is able and willing to comply with the protocol and study procedures.
9. Subject has negative test results for drugs and alcohol at screening and is able and willing to abstain from marijuana and alcohol use for 4 days before Day 1 and throughout the study. Note that a positive screening result for marijuana is acceptable provided the subject will abstain for the study as described above.
10. Subject does not use nicotine or has quit using nicotine for at least 6 months before the first dose of study gel and will not use nicotine throughout the study.

■ [REDACTED]

■ [REDACTED]

■ [REDACTED]

■ [REDACTED]

15. Subject has participated in an investigational drug study within 30 days before Screening.
16. Subject is a member or a family member of the professional or ancillary personnel involved in the study.
17. Subject has participated in other clinical trials for K-285.
18. Subject has abnormal findings or assessments that are clinically noteworthy.
19. Subject who, in the opinion of the investigator, should not participate in the study.

Statistical Analysis:

In general, assessments with continuous outcomes will be summarized using the descriptive statistics n, mean, standard deviation (SD), median, minimum and maximum. For assessments with categorical outcomes, frequency counts and percentage will be calculated. Detailed statistical methodology will be presented in a separate statistical analysis plan.

Study Populations:

Three analysis populations will be evaluated:

- The full analysis set (FAS) will include all randomized subjects who have a baseline pain score, and at least 1 study gel applied
- The per-protocol set (PPS) will include all randomized subjects who have a baseline pain score, at least 1 study gel applied, and no major protocol violations.
- The safety set will include all subjects who have at least 1 study gel applied.

Primary Efficacy Analysis:

The primary analysis population is the FAS. The primary analysis will be repeated using the PPS. [REDACTED]

[REDACTED]. If there exist missing VAS values to be imputed, any such values will be imputed before calculating the SPID. After calculating the SPID, an analysis of covariance (ANCOVA) model will be applied for the primary endpoint with gender and treatment as main effects and baseline pain as a covariate.

Secondary Efficacy Analyses:

A mixed effect model repeated-measures (MMRM) with the same main effects and covariate will be applied to the PID while standing and PID at rest to investigate treatment differences.

[REDACTED] The time to first dose of rescue medication, will be analyzed using the Kaplan-Meier method to estimate the survival distribution function.

Safety:

The safety endpoint data will be summarized for the safety set. Adverse events will be coded using the latest version of the Medical Dictionary for Regulatory Activities (MedDRA). Adverse events and serious AEs (SAEs) will be summarized by treatment group for overall number of AEs, severity, and relationship to study gel. The incidence of AEs will be summarized by body system and treatment group. The incidence of treatment-emergent AEs (TEAEs) will also be summarized by system organ class and preferred term. Clinical laboratory results will be summarized by treatment group along with change from Baseline. Vital sign measurements will be summarized by group and time point along with change from Baseline. All AE, clinical laboratory, vital sign, physical examination, study gel application site reaction, study gel use and concomitant medication use will be presented in data listings.

[REDACTED]

Sample Size Calculation:

The parameters are conservatively estimated based on the DOMS study with [REDACTED] gel. The between-group difference in the mean [REDACTED] is 11.07 with a SD of 25.62. To have statistical power of 90%, 113 subjects per group are required. Taking into account information loss caused by missing data, it is estimated that 120 subjects need to be treated with each study gel.

TABLE OF CONTENTS

| | |
|---|------------|
| INVESTIGATOR’S STATEMENT | ii |
| SIGNATURE PAGE | iii |
| PROTOCOL SYNOPSIS | iv |
| LIST OF ABBREVIATIONS AND DEFINITION OF TERMS | xv |
| 1.0 INTRODUCTION AND RATIONALE FOR DOSE SELECTION | 1 |
| 1.1 BACKGROUND INFORMATION | 1 |
| 1.2 RATIONALE FOR STUDY AND DOSE SELECTION | 2 |
| 2.0 STUDY OBJECTIVES | 4 |
| 2.1 PRIMARY OBJECTIVE | 4 |
| 2.2 SECONDARY OBJECTIVES..... | 4 |
| 2.3 PRIMARY EFFICACY ENDPOINT | 4 |
| 2.4 SECONDARY EFFICACY ENDPOINTS | 4 |
| 2.5 SAFETY ENDPOINTS | 5 |
| 3.0 STUDY DESCRIPTION | 6 |
| 3.1 STUDY DESIGN | 6 |
| 4.0 SUBJECT ELIGIBILITY AND WITHDRAWAL CRITERIA | 14 |
| 4.1 INCLUSION CRITERIA | 14 |
| 4.1.1 Pre-exercise Inclusion Criteria..... | 14 |
| 4.1.2 Post-exercise Randomization Inclusion Criteria:..... | 15 |
| 4.2 EXCLUSION CRITERIA | 15 |
| 4.3 DISCONTINUATION AND WITHDRAWAL CRITERIA..... | 16 |
| 4.3.1 Discontinuation due to an Application Site Reaction | 17 |
| 5.0 PROCEDURES FOR EFFICACY AND SAFETY EVALUATIONS | 18 |
| 5.1 EFFICACY EVALUATIONS | 18 |
| 5.1.1 Pain Intensity | 18 |
| 5.1.1.1 Visual Analog Scale..... | 18 |
| 5.1.1.2 Categorical Pain Scale | 18 |

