| ASSESSMENTS PERFORMED | Screening Visit | Exercise Visit | Period 1 | | | Period 2 | | | | EOS Visit/ET ^k | Follow-up call |
|--|-----------------|----------------|------------|-------------|--------------|---------------|--------------|----------------|-------|---------------------------|----------------------|
| | | | In patient | Out patient | Safety Visit | Out patient | Safety Visit | Out patient | | | |
| Day | -30 to -2 | -1 | 1 | 2 | 3-8 | 8 (±1 day) | 9-14 | 15 (±1 day) | 16-22 | 8 or 22 (+1 day) | 15 or 29 (±1 day) |
| Informed consent | X | | | | | | | | | | |
| Demography | X | | | | | | | | | | |
| Medical/medication history | X | X | | | | | | | | | |
| Pre-exercise inclusion criteria, exclusion criteria | X | X | | | | | | | | | |
| Admission to clinic ^a | | | X | | | | | | | | |
| Discharge from clinic ^a | | | | X | | | | | | | |
| Visit to clinic (one day) | X | X | | | | X | | X | | X | |
| Telephone Call (Days 5, 11, 18, and Day 15 or 29) ^b | | | | | X | | X | | X | | X |
| Pre-exercise pain assessment (paper VAS) | | X | | | | | | | | | |
| DOMS induction exercise | | X | | | | | | | | | |
| e-diary, study training | | X | | | | | | | | | |
| Issue e-diary | | | X | | | | | | | | |
| eVAS qualifying pain assessments ^c (e-diary) | | | X | | | | | | | | |

| ASSESSMENTS PERFORMED | Screening Visit | Exercise Visit | Period 1 | | | Period 2 | | | | EOS Visit/ET ^k | Follow-up call |
|---|-----------------|----------------|------------|-------------|-------------|---------------|-------------|----------------|-------------|---------------------------|----------------------|
| | | | In patient | Out patient | Out patient | Safety Visit | Out patient | Safety Visit | Out patient | | |
| Day | -30 to -2 | -1 | 1 | 2 | 3-8 | 8 (±1 day) | 9-14 | 15 (±1 day) | 16-22 | 8 or 22 (+1 day) | 15 or 29 (±1 day) |
| Categorical qualifying pain assessments ^c (e-diary) | | | X | | | | | | | | |
| Post-exercise inclusion criteria | | | X | | | | | | | | |
| Randomization | | | X | | | | | | | | |
| Height and weight | X | | | | | | | | | | |
| Vital signs ^d | X | X | X | X | | X | | X | | X | |
| Electrocardiogram | X | X | | | | | | | | X | |
| Physical examination | X | X | | | | X | | X | | X | |
| Skin examination / assessment at study gel site | X | X | X | X | | X | | X | | X | |
| Pregnancy test ^e | X | X | | | | | | | | X | |
| Urine drug screen and alcohol test | X | X | | | | | | | | | |

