- c VAS and categorical qualifying pain assessments will be performed on both legs within 24-30 hours of exercise to induce DOMS. Pain intensity assessments (eVAS, Perceptible Pain Relief, and Meaningful Pain Relief) will be performed for the study leg and non-study leg at rest and while standing using a 0-100 point eVAS on Day 1 at Baseline (0 hours) and at ██████████ after the first study gel application. Baseline (0 hours) is the time point for the first study gel application; a time window of +30 minutes will be allowed between qualifying pain assessments (qualifying post-exercise inclusion criteria) and first study gel application (0 hour). The following time windows will be allowed for each pain assessment (eVAS, Perceptible Pain Relief, and Meaningful Pain Relief) time point: ±15 minutes for assessments from 1 to 12 hours (Day 1), -20 minutes to +30 minutes for assessments at 18 through 24 hours (Day 2), and -20 minutes to +1 hour for assessments at 36 to 168 hours (Day 2 to 8). Time to perceptible and meaningful pain relief will be recorded by subjects in their e-diary until achieved in Period 1. When study gel application and pain assessment occur at the same time point, pain assessments will be performed before study gel application.

- d Vital sign measurements will include systolic blood pressure, diastolic blood pressure, pulse rate, respiratory rate, and oral body temperature. Blood pressure and pulse rate will be measured after the subject has been resting in the supine position for at least 5 minutes.
- e Serum pregnancy test at Screening and urine pregnancy test at Exercise visit, EOS Visit (Day 8 or Day 22) (females only).
- f Photographic and residue evaluations of the application site will be performed before the [REDACTED] study gel applications on Day 2.
- g Beginning with the [REDACTED] when an application site reaction is observed at the clinical site, photographs of the application site will be taken by site staff to visually document the skin condition at the site of gel application. If needed, the photographs will be periodically taken to follow-up the application site reaction. If an application site reaction is observed at home, photographs of the application site will be taken by site staff when subject returns to the clinical site. All photographs should be taken prior to gel application [REDACTED]
- h [REDACTED]
[REDACTED]
[REDACTED]

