9.5 Vital Signs, Physical Measurements, and Physical Examinations

9.5.1. Vital Signs and Physical Measurements

Vital signs will be collected at screening, Day 1 prior to study gel administration (Day -1), Day 1, 2 (period 1), Day 8, 15 (period 2), and at the end of study visit on Day 8 or 22 (± 1 day).

Observed values and changes from baseline will be summarized using mean and change-from-baseline descriptive statistics for each treatment group, for the following measurements: systolic blood pressure (mmHg), diastolic blood pressure (mmHg), pulse rate (beats/minute), and oral body temperature. Blood pressure and pulse rate will be measured after the subject has been resting in the supine position for at least 5 minutes.

CONFIDENTIAL Page 23 of 33

Body weight and height will be measured, and BMI will be calculated during the screening visit only. These values will be summarized along with other baseline characteristics for each treatment group. The number and percentage of subjects with potential clinically significant findings listed in Table 2 will be summarized for each treatment group. Vital signs will be displayed in a by-subject listing.

Table 2. List of Potential Clinically Significant Ranges for Vital Sign Parameters

Variable Name	Low	High
Systolic blood pressure	≤86 mm Hg OR a decrease of ≥25 mm Hg from baseline	≥200 mm Hg OR an increase of ≥25 mm Hg from baseline
Diastolic blood pressure	≤48 mm Hg OR a decrease of ≥20 mm Hg from baseline	≥110 mm Hg OR an increase of ≥20 mm Hg from baseline
Pulse	<45 bmp¹ OR a decrease of ≥25 bpm from baseline	>105 bpm and increase ≥25 bpm from baseline OR >125 bpm

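### SAP 9.5.1 leaves respiratory rate out of the by-group vital-sign summary that the protocol calls for; the safety text on weight also needs a wording correction

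*Protocol*

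**What the plan says.** **Respiratory rate in the protocol.** The Synopsis and section 2.5 (headed as safety endpoints) both list "vital sign measurements (systolic blood pressure, diastolic blood pressure, pulse rate, respiratory rate, and oral body temperature), ECG, physical examination findings including weight". Table 2, footnote d, repeats the five measures: "Vital sign measurements will include systolic blood pressure, diastolic blood pressure, pulse rate, respiratory rate, and oral body temperature". Section 5.2.3 does the same. On analysis, the Synopsis says "Vital sign measurements will be summarized by group and time point along with change from Baseline", and section 11.6 says the same in nearly the same terms. Neither place exempts a parameter.

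**Respiratory rate in the SAP.** Section 9.5.1 gives observed values and changes from baseline by treatment group "for the following measurements: systolic blood pressure (mmHg), diastolic blood pressure (mmHg), pulse rate (beats/minute), and oral body temperature". Respiratory rate is not there. The same section also promises a by-subject listing of vital signs, with no parameter restriction (Listing 16.2.7.2). Table 14.6.1 is planned by treatment arm, and its title names no parameters.

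**Weight.** The protocol safety text attaches weight to the physical examination findings. Protocol Table 2 schedules height and weight at Screening alone. SAP 9.5.1 agrees: "Body weight and height will be measured, and BMI will be calculated during the screening visit only". It then summarizes them with the other baseline characteristics.

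**The concern.** Safety and tolerability against menthol gel is a secondary objective in both documents. The protocol says what the safety report will contain, and the SAP should deliver it or explain any departure. Here the SAP narrows the list without comment. A programmer working from 9.5.1 would build a four-parameter table, and the report would lack a by-arm summary that the protocol promised on data the trial collected. If someone then asked for respiratory rate, SAP section 1 would require the addition to be labelled post hoc, although the protocol had specified it in advance.

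The weight wording raises a smaller question. Listed among safety endpoints, weight looks like something to be followed on treatment, but nothing after Screening is scheduled.

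**Working it through.** The plan gives no figure to reproduce on this point, so the check sets the texts side by side.

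**Step 1. The vital-sign lists.**

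| Measure | Protocol 2.5 and Synopsis | Collected (Table 2, footnote d; 5.2.3) | SAP 9.5.1 by-group summary |
|---|---|---|---|
| Systolic pressure | yes | yes | yes |
| Diastolic pressure | yes | yes | yes |
| Pulse rate | yes | yes | yes |
| Respiratory rate | yes | yes | **no** |
| Oral temperature | yes | yes | yes |

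The protocol names 5 and the SAP summarizes 4. 5 − 4 = 1 missing, and 1/5 = 20%. The missing item is respiratory rate. The SAP sentence is complete and shows no gap, so blacked-out text does not explain the omission.

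**Step 2. Whether the data exist.** Protocol Table 2 and section 6.3 schedule vital signs as follows:

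- Subjects dosed for 1 week: Screening, Day -1, Day 1, Day 2 and Day 8 (EOS), which is 5 visits. At least Day 2 and Day 8 follow the first application.
- Subjects dosed for 3 weeks: Screening, Day -1, Day 1, Day 2, Day 8, Day 15 and Day 22 (EOS), which is 7 visits. At least Days 2, 8, 15 and 22 follow it.

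Day 1 is not counted as post-application because the schedule does not fix its timing relative to the first application. In both arms there are values before and after gel, so change from baseline can be computed.

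**Step 3. Which SAP text governs.** SAP section 3 has a general rule that all continuous assessments are summarized, which would cover respiratory rate. The same section says that where a specific section departs from the general policies, the specific section prevails. The named list in 9.5.1 is the specific rule, so it controls.

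**Step 4. Whether another SAP passage restores it.** Section 9.1 and the title of Table 14.6.1 refer to vital signs generally and name no parameters. The rows shown in the SAP table of potentially clinically significant ranges cover systolic pressure, diastolic pressure and pulse. None of these adds respiratory rate to the by-group summary.

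**Step 5. Weight.** Scheduled measurements: 1 (Screening). Scheduled measurements after the first application: 0. The repeated physical examination (Protocol 5.2.5) does not list weight among its components. Protocol 5.3.1 and SAP 6.1 both treat weight as a baseline characteristic.

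**The case against.** The best defence is that this is a drafting slip with little consequence. The title of Table 14.6.1 is unrestricted, the general rule in SAP section 3 covers every continuous assessment, and 9.5.1 never says that respiratory rate is excluded. A sensible programmer might include it anyway. That may be so, and nothing shows that the omission was deliberate. But the precedence rule favours the narrower list, and a plan should not depend on the programmer overriding it.

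Two stronger readings are tempting, and the documents support neither.

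- A reader might infer that respiratory rate cannot be compared between gels. It can: it is recorded in both arms before and after application and is covered by the by-subject listing. What the SAP lacks is the planned group summary. The by-subject listing preserves the data but does not replace that summary.
- A reader might infer that weight is a safety endpoint the trial fails to evaluate. The text where it appears is an inventory of safety assessments that also includes gel use and concomitant medication. No passage promises a post-treatment weight or a change in weight. The SAP safety-outcome lists (4.2 and 9.1) do not name it, and every operative passage consistently places it at Screening. The fault is a loose phrase.

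**Conclusion.** The point holds for respiratory rate. SAP 9.5.1 omits one of the five vital signs that the protocol names, collects and says will be summarized by group and time point with change from baseline, and no other passage corrects this. The conclusion rests on reading the 9.5.1 list as closed, which the SAP's own precedence rule supports.

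The severity is minor. The omission concerns a descriptive safety table. It touches no test, decision rule, primary analysis or sample size, and clinical impact is probably small for a topical gel used for 1 to 3 weeks. The weight issue is a wording inconsistency between the safety text and an otherwise consistent Screening-only schedule.

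**What to change.** 1. Add respiratory rate (breaths/minute) to the list in SAP 9.5.1 and as a parameter in Table 14.6.1. The cost is one more block of rows in an existing table, from data already collected.
2. For weight, delete its mention from the safety text in the protocol Synopsis and 2.5, or state in the SAP or study report that weight is a baseline characteristic only. The cost is a line of text.

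Adding a weighing at the end-of-study visit is not a usable alternative. SAP 2.2.6 records that the futility rule was met and that the 126 subjects already randomized form the final analysis, so new collection could not cover that population.
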